# AIM 1: Determine the impact of timed rectal evacuation on anorectal dysfunction in MS patients

We will conduct a four week, single-center, randomized, double-blind placebo controlled clinical trial designed to assess the efficacy of timed rectal evacuation in improving the subjective global assessment of bowel symptoms in a cohort of patients with mild-to-moderate severity MS disease. Patients will be randomized 1:1 to administer either placebo or bisacodyl 10 mg rectal suppositories every other day during the 4 week trial. The primary endpoint will be the change in patients' rating of bowel symptom severity (10 point rating scale) at end of 4 weeks compared to baseline values. We will define an adequate treatment response as greater than a 30% reduction in symptom severity using an intention-to-treat analysis.

AIM 2: Determine the predictors of treatment response and impacts on quality of life

We plan to collect information on the patients' assessed severity of baseline and treatment-associated anorectal dysfunction, their impact on quality of life, as well as daily bowel diaries. Patients also will undergo anorectal sensory and manometric testing as a part of their routine clinical care. Enrolled patients that complete the study will be assessed for study medication compliance. All of these measures will be used to explore factors that are associated with treatment response. Changes in assessments of anorectal dysfunction-related quality of life will serve as key secondary end-points.

This proposal will significantly advance MS care and management by developing the evidence to support the adoption of a simple, safe, and cost-effective clinical treatment algorithm for anorectal dysfunction in the MS population. This paradigm for anorectal dysfunction management could be applicable to a majority of MS patients, and the treatment algorithm could be introduced to patients by nurses or mid-level clinical providers during points of routine MS patient care. Importantly, the treatment could be effectively accomplished by most patients and their caregivers at home. The findings of this investigation could also have a broader influence on care models for anorectal dysfunction associated with a range of other neurological illnesses, such as Parkinson's Disease, ALS, or stroke.

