Study flow: A schematic of the study flow is shown in the attached figure. All patient encounters, referrals, and tests are integrated into the flow of routine clinical care at UPMC. Recruited patients will meet with the study coordinator in an in-person meeting to discuss the details of the study and obtain informed consent (Kaufman Building MS Clinic). At that time (Phase 1), additional measures of baseline bowel symptom severity and bowel-related quality of life (QOL) will be obtained by standardized questionnaires (see below). The study coordinator will provide patients with instructions on maintaining a daily bowel diary (see Study Measures below), and then initiate referrals for anorectal function testing in the DDC and a later follow-up appointment with the PI/Co-PI ("NeuroGI"). The consent process, baseline questionnaires, and instructions on bowel diary are unlikely to take more than 1 hour of time.

During the next 2-4 weeks after study entry, patients will complete the baseline daily bowel diary.

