During Phase 2, patients will meet the PI / Co-PI in the UPMC Digestive Disorders Center (DDC) for anorectal function testing (anorectal sensory and High Resolution Anorectal Manometry (HRAM) testing), which typically takes about 45 minutes. This is a one time, routine test that is performed in patients with anorectal dysfunction. It involves the transanal placement of a thin manometry catheter with inflatable balloon into the rectum. The patients' threshold to first sensation of rectal filling, urgency, and pain, basal anal resting pressure, voluntary anal squeeze pressure, and the rectal-anal inhibitory reflex (RAIR) to rectal distention and during simulated strain, as well as the ability to evacuate a 50 cc volume rectal balloon within one minute are all recorded variables and constitute normal components of such testing. The PI/Co-PI will meet with patients in the DDC GI lab around the time of the anorectal testing, and based on the clinical assessment of dominant bowel symptoms, provide patients with guidance on baseline interventions (either laxative or anti-diarrheal use). For example, the use of oral therapies is predicated on patients' typical stool form (using the Bristol Stool Scale 1-7) - the goal is to achieve a typical bowel movement of a 3-5 in consistency. Patients with Bristol 1-2 stools (hard) will use 8.5 - 42 grams of PEG-3350 laxative per day, while those with Bristol 6-7 (loose) will use 0.5 - 4 grams of loperamide per day, titrated to the goal. At the end of Phase 2 visit, patients will be given instructions on study medication use and will obtain the study drug (double-blinded; study drug "blister" packets would have been previously randomized by the pharmacy and delivered to the DDC). Patients will be encouraged to continue daily bowel diaries for the ensuing 4 weeks of the study trial period. Phase 2, including the physiological testing assessment and meeting with the PI/Co-PI, should take about 1.5 hours in total.

During the next 4 weeks, patients will use recommended oral therapies in addition to the every other day use of the rectal suppository study medication. They will record events in their daily bowel diary.

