Finally in Phase 3, after the 4 week study period, patients will meet with the study coordinator to collect unused study medication and completed bowel diaries, and then undergo final reassessments of bowel dysfunction severity and QOL measures. This process could take up to 1 hour. After the questionnaires are completed, patients and the PI/Co-PI will be debriefed (i.e. study arm allocation will be revealed) before having a routine followup clinic visit (continuity of care).

- 1) The study coordinator will identify and screen potential study subjects (by accessing the "UPMC Multiple Sclerosis and Related Disorders Registry" (PRO12010609) to identify prospective subjects), coordinate the informed consent process with the PI/Co-PI, collect intake questionnaires, and provide instruction on bowel diaries (Phase 1). The coordinator will schedule referrals for anorectal function testing and follow-up DDC visit, and contact patients during the 4-week trial period to verify compliance. Finally, the coordinator will collect bowel diaries and remaining medications at study end, administer study exit questionnaires, and then debrief subjects and the PI/Co-PI once the blind is broken (Phase 3).
- 2) DDC GI nursing staff routinely performs HRAM studies and will do so in this study. The PI/Co-PI will be involved in clinical care and recommendations both during Phase 2 and Phase 3 (and beyond).
- 3) MS Physicians will be involved in initial identification of potential subjects and all MS-related continuity of care.
- 4) Falk Pharmacy serves UPMC for clinical trials, and staff will ensure the 1:1 randomization and distribution of either twenty placebo or biscodyl 10 mg rectal suppositories (used every other day over 4 weeks during the study period). Falk Pharmacy staff is experienced in running clinical trials and maintaining double-blind study conditions between subjects and investigators. Patients will receive a slight excess number of suppositories in order to assess study medication compliance at trial end.

STUDY MEASURES: We plan to obtain the following information from all enrolled patients:
1) Primary Patient-Reported Outcome Measure: "Using a scale of 1 to 10 (1 being no problem and 10 being maximally impactful symptoms), how would you rate the severity of your bowel symptoms over the past 2 weeks?"

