- 2.14.2 Are you requesting a waiver of the requirement to obtain written HIPAA authorization for the collection of the PHI?
  - \* No

[reviewer notes-]

- 2.15 Does this research study involve the long-term storage (banking) of biological specimens?
  - \* No

[reviewer notes¬]

- 2.16 Will research participants be asked to provide information about their family members or acquaintances?
  - \* No

[reviewer notes¬]

2.17 What are the main outcome variables that will be evaluated in this study?

PRIMARY END POINT: The primary end-point of the randomized clinical trial is a greater than 30% improvement in patients' subjective global assessment of bowel symptom severity after 4 weeks based on the answer to the following question: "Using a scale of 1 to 10 (1 being no problem and 10 being maximally impactful symptoms), how would you rate the severity of your bowel symptoms over the past 2 weeks?"

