#### SECONDARY END POINTS:

1) Daily Bowel Diaries – patients will record the consistency (Bristol Stool Scale, 1-7), number of bowel movements (BM), and occurrence of any fecal incontinence (FI) episodes each day. This data will be used to abstract BM and FI weekly frequency, as well as the mean change in stool consistency during the study period.

- 2) Patient Assessment of Constipation Symptom Questionnaire (PAC-SYM)
- 3) Fecal Incontinence Severity Index (FISI)
- 4) Patient Assessment of Constipation QOL (PAC-QOL)
- 5) Rockwood Fecal Incontinence Quality of Life Scale (FIQL)
- 6) SF-36 health status questionnaire
- 7) Study Medication Compliance
- 8) Anorectal Sensory and High Resolution Anorectal Manometry Testing: First sensation of rectal filling, urgency, and pain, basal anal resting pressure, voluntary anal squeeze pressure, and the rectal-anal inhibitory reflex (RAIR) to rectal distention and simulated strain, as well as the ability to evacuate a 50 cc volume rectal balloon within one minute.
- 2.18 Describe the statistical approaches that will be used to analyze the study data.
  - \* Addressed below:

Categorical data will be analyzed using Fisher's Exact tests for differences in proportions. Continuous data will be analyzed using Student's t-tests to detect differences in group means, with Bonferroni correction for multiple comparisons. We will use logistic regression to determine the factors that predict treatment responses.

A p<0.05 will be used as the threshold for statistical significance in all cases.

POWER ANALYSIS/SAMPLE SIZE: It is generally regarded that a 3-point reduction represents a clinically meaningful change using such a 10 point scale, and similar research studies using patient-reported outcomes have reported standard deviations ranging around ~2.5 points. However, we do not have baseline data to estimate variance, and thus we took a conservative estimate with an expected standard deviation of 4 points. Given these assumptions, we will need 28 patients in each study arm to detect at least a 30% reduction in symptom severity, with a power of 0.80, alpha=P<0.05 in a two-tailed analysis.

[reviewer notes-]

- 2.19 Will this research be conducted in (a) a foreign country and/or (b) at a site (e.g., Navajo Nation) where the cultural background of the subject population differs substantially from that of Pittsburgh and its surrounding communities?
  - \* No

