3.8 Does this research study involve neonates of uncertain viability or nonviable neonates?

\* No

[reviewer notes¬]

- 3.9 Fetal Tissues: Does this research involve the use of fetal tissues or organs?
  - \* No

[reviewer notes¬]
--->

3.10 What is the total number of subjects to be studied at this site, including subjects to be screened for eligibility?

Note: The number below is calculated by summing the data entered in question 3.11. Any additions or changes to the values entered in 3.11 will be reflected in 3.10.

- \* 400
- 3.11 Identify each of the disease or condition specific subgroups (include healthy volunteers, if applicable) that will be studied.

Click on the "Add" button and specify for each subgroup:

- 1) how many subjects will undergo research related procedures at this site; and
- 2) if applicable, how many subjects will be required to undergo screening procedures (e.g., blood work, EKG, x-rays, etc.) to establish eligibility. Do Not include subjects who will undergo preliminary telephone screening.

\*

Subgroup	Number to undergo research procedures	Number to undergo screening procedures
View MS patients	70	400

- 3.12 Provide a statistical justification for the total number of subjects to be enrolled into this research study at the multicenter sites or this site.
  - \* Described below:

The primary outcome measure is the group mean difference in subjective severity ratings of bowel symptoms using a 10 point scale. It is generally regarded that a 3-point reduction represents a clinically meaningful change using such a scale, and similar

Section: Section 3 - Human Subjects

research studies using patient-reported outcomes have reported standard deviations ranging around ~2.5 points on a 10 point scale. However, we do not have baseline data in this population to estimate variance, and thus we took a conservative estimate with an expected standard deviation of 4 points. Given these assumptions, we will need 28 patients in each study arm to detect at least a 3 point reduction in symptom severity, with a power of 0.80, alpha=P<0.05 in a two-tailed analysis.

Thus, the study is adequately powered if enrollment reaches 56 patients. However, to ensure adequate numbers in an intention-to-treat analysis, we will plan for a ~20% patient drop-out rate. Therefore, we will aim to enroll 70 patients in total.

[reviewer notes¬]

3.13 Inclusion Criteria: List the specific criteria for inclusion of potential subjects.

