If the subject withdraws from the study after having passed Phase 1 (i.e. baseline measures of bowel dysfunction and quality of life), we would keep the data for an "intention-to-treat" analysis (with the assumption of an non-response). If a subject has not completed Phase 1, then the research data will be destroyed.

**5.17** Following the required data retention period, describe the procedures utilized to protect subject confidentiality. (e.g., destruction of research records; removal of identifiers; destruction of linkage code information; secured long-term retention)

We will destroy primary research records with any identifiers, but may opt to retain deidentified electronic data on a secured server for future re-analysis. Per University of Pittsburgh guidelines, research records will be archived for a minimum of seven years after final reporting or publication of a project.

Section: Section 6 - Costs and Payments

[reviewer notes-]

6.1 Will research subjects or their insurance providers be charged for any of the procedures (e.g., screening procedures, research procedures, follow-up procedures) performed for the purpose of this research study?

Yes; charges will be billed only for procedures performed as part of the subject's routine clinical care as addressed in question 2.9

[reviewer notes-]

6.2 Will subjects be compensated in any way for their participation in this research study?

\* No

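### Continuous outcomes measured before and after treatment are compared by unadjusted t-tests; adjusting each for its own baseline would give more precision from data already collected

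*Combined protocol and SAP*

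**What the plan says.** Section 2.18 gives one rule for continuous outcomes: "Continuous data will be analyzed using Student's t-tests to detect differences in group means", with a Bonferroni correction. Categorical outcomes get Fisher's exact test. The only regression in the plan is a logistic model for predictors of response, which is not a baseline-adjusted comparison of the arms. Section 2.18 does not say whether the t-tests use week-4 values or changes.

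Baseline values are collected before study drug. Section 2.6 (Study flow, Phase 1) says: "At that time (Phase 1), additional measures of baseline bowel symptom severity and bowel-related quality of life (QOL) will be obtained by standardized questionnaires". A daily diary is then kept for 2-4 weeks before treatment and continued through the 4 treatment weeks. At Phase 3 patients "undergo final reassessments of bowel dysfunction severity and QOL measures". SF-36 is not named at Phase 1, but the Phase 3 reassessment of quality of life and section 5.16, which describes Phase 1 as "baseline measures of bowel dysfunction and quality of life", imply that it is given then.

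The severity rating appears in three forms:

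- Section 1.2, Aim 1: "The primary endpoint will be the change in patients' rating of bowel symptom severity (10 point rating scale"), compared with baseline at 4 weeks.
- Section 3.12: "The primary outcome measure is the group mean difference in subjective severity ratings of bowel symptoms using a 10 point scale".
- Section 2.17: "The primary end-point of the randomized clinical trial is a greater than 30% improvement".

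The first two are continuous and fall under the t-test rule. The third is a responder definition and falls under Fisher's test.

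**The concern.** A t-test on week-4 scores ignores baseline. A t-test on change uses baseline, but with its weight fixed at 1. ANCOVA estimates the weight from the data. Under randomisation all three target the same mean difference, and with equal variances at the two visits ANCOVA has the smallest sampling variance for any correlation strictly between 0 and 1, apart from the loss of one degree of freedom.

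This matters here because the trial is small, section 2.18 admits that no baseline data exist to estimate variance, and the continuous secondary outcomes are tested at a Bonferroni-reduced level, where wasted precision costs most. Stating the model in advance also avoids a later choice between week-4 and change-score tests: with baseline in the model, both give the same treatment estimate.

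**Working it through.** **Inputs from the documents** (2.18, 3.12, Aim 1): difference 3 points; SD 4, not stated whether of the score or of the change; cited SD in similar studies about 2.5; two-sided alpha 0.05; power 0.80; 1:1 allocation; 28 per arm; 70 enrolled after about 20% drop-out.

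**Assumed, because the documents do not give it:** the correlation r between baseline and week-4 values, shown over a range, and equal variance at both visits.

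**1. The plan's own figure.** n per arm = 2 × SD² × (1.960 + 0.842)² / 3² = 2 × 16 × 7.849 / 9 = 27.9, so 28. Normal-approximation power is 0.801. The stated N reproduces and contains no allowance for baseline. With the noncentral t (54 df), power at 28 per arm is 0.787. The 95% CI half-width is t(0.975, 54) × 4 × √(2/28) = 2.005 × 4 × 0.2673 = 2.14.

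**2. ANCOVA residual SD.** Residual variance relative to a change-score t-test is (1 + r)/2; relative to a week-4 t-test it is 1 − r². So:

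- if SD 4 is the SD of change, residual SD = 4√((1 + r)/2);
- if SD 4 is the SD of the score, residual SD = 4√(1 − r²).

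Power then uses the noncentral t with 53 df.

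| Reading of SD 4 | r | Residual SD | Power | CI half-width |
|---|---|---|---|---|
| Unadjusted t-test | – | 4.00 | 0.787 | 2.14 |
| SD of change | 0.3 | 3.22 | 0.927 | 1.73 |
| SD of change | 0.5 | 3.46 | 0.889 | 1.86 |
| SD of change | 0.6 | 3.58 | 0.869 | 1.92 |
| SD of score | 0.3 | 3.82 | 0.823 | 2.05 |
| SD of score | 0.5 | 3.46 | 0.889 | 1.86 |
| SD of score | 0.7 | 2.86 | 0.971 | 1.53 |

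Under the change reading the implied score SD is 4/√(2(1 − r)) = 3.38, 4.00 and 4.47 at r = 0.3, 0.5 and 0.6. The largest possible SD on a 1-10 scale is (10 − 1)/2 = 4.5, so r cannot exceed 1 − 16/(2 × 4.5²) = 0.605. The range stops at 0.6 for that reason.

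**3. At the cited SD of 2.5.** Unadjusted power is 0.993, so only the interval improves. From an unadjusted 1.34, the half-width falls to 1.28, 1.16 or 0.96 (score SD) or to 1.08, 1.16 or 1.24 (change SD) at r = 0.3, 0.5 or 0.7.

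**4. Secondary outcomes.** Assume five questionnaire tests, so alpha = 0.05/5 = 0.01, with 28 per arm. At r = 0.5 both readings multiply the standardised effect by 1/√0.75.

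- For an assumed effect of 0.5 SD, power goes from 0.223 to 0.315.
- For 0.75 SD, it goes from 0.557 to 0.713.
- Against change scores, the 0.5 SD result varies with r: 0.372, 0.315, 0.271 and 0.253 at r = 0.3, 0.5, 0.7 and 0.8.

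**5. Unequal variances.** Let k be the ratio of week-4 SD to baseline SD. The variance saved against a change-score t-test is 1 − k²(1 − r²)/(1 + k² − 2rk). At r = 0.5, 0.6 and 0.7 this is 11%, 6% and 2% for k = 1.25, and 4%, 0.7% and 0.2% for k = 1.5. With k = 1 it is (1 − r)/2 = 25%, 20% and 15%.

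**The case against.** The strongest reply is that much of the baseline information may already be in use. Aim 1 defines the severity endpoint as a change, Aim 2 makes changes in bowel-related quality of life key secondary endpoints, and the diary outcome includes mean change in stool consistency. Only section 3.12 leaves the week-4 reading open, so the largest gain (to 0.97) rests on the less supported reading. This stands: the change-score rows are the better guide for severity.

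Against change scores the gain also depends on equal variances. Section 3.13 enrols only patients who already have bowel symptoms, so baseline spread could be narrower than week-4 spread. Step 5 of the working shows that the gain could then nearly vanish. This also stands, but it shrinks the gain without reversing it, beyond one degree of freedom, and a ratio below 1 would enlarge it.

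Next, SD 4 is deliberately conservative. At SD 3 the unadjusted power is 0.957, and at 2.5 it is 0.993. Also, 70 are enrolled: at 35 per arm with SD 4 the t-test has power 0.871, ignoring any dilution from withdrawals. So 0.787 is not a shortfall in the plan; it is the reference for the comparison.

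Finally, if the responder definition in 2.17 governs, no primary analysis changes. That is correct, and the case then rests on the secondaries. ANCOVA would also need a rule for missing week-4 values and could fit poorly to incontinence counts with many zeros, but the planned t-test has both difficulties too.

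**Conclusion.** The concern holds, as a loss of efficiency. The t-test is valid, the stated 28 per arm is right for it, and nothing here is a bias. No section adjusts the comparison of the arms for baseline, although the values are collected.

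At r = 0.5 with equal variances, adjustment saves 25% of the variance under either reading, taking power from 0.787 to 0.89 at SD 4. Over the ranges shown, adjusted power is 0.87 to 0.93 if SD 4 is the SD of change, and 0.82 to 0.97 if it is the SD of the score. The size rests on an assumed r and on equal variances. The gain is small if r is low against a week-4 test, if r is high against a change test, or if week-4 scores are much more variable than baseline scores. If the SD is nearer 2.5, the severity comparison gains only a narrower interval.

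The point does not reach the responder version of the primary endpoint, compliance (no baseline) or manometry, of which section 2.6 says "This is a one time, routine test that is performed in patients with anorectal dysfunction". The change should be made, but the trial is not invalid without it.

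**What to change.** In section 2.18, for the severity rating in its continuous form and for each continuous secondary outcome with both a baseline and an end-of-treatment value, replace the t-test with a linear model of the end-of-treatment value on arm and that outcome's own baseline. Report the adjusted difference with its 95% CI. Use the Phase 1 rating as the severity baseline, consistent with section 5.16, and the pre-treatment diary period as the diary baseline. Include SF-36 if it is confirmed as given at Phase 1. Keep Fisher's exact test for the responder version, and leave compliance and manometry outside the rule.

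The cost is one sentence and one degree of freedom per model (53 instead of 54 at 28 per arm). Visits, forms and the responder definition are unchanged. The gain should protect power, particularly for the Bonferroni-corrected secondaries, and should not be used to reduce enrolment. It would help to state in 2.18 and 3.12 whether SD 4 refers to the score or the change.

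### Aim 2 makes bowel-related quality of life the key secondary end point, but 2.17 leaves PAC-QOL and FIQL unranked and 2.18 names plain Bonferroni without saying which tests share it

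*Combined protocol and SAP*

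**What the plan says.** Section 1.2, Aim 2, ranks the secondary outcomes: "Changes in assessments of anorectal dysfunction-related quality of life will serve as key secondary end-points". It names no instrument. PAC-QOL and FIQL are the two bowel-specific quality-of-life scales among the study measures, so they are the natural reading.

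Section 2.17 lists eight secondary end points without rank. PAC-QOL is item 4 and FIQL item 5. Item 7 is "Study Medication Compliance" and item 8 is anorectal sensory and manometric testing. Of that testing, 2.6 (Phase 2) says "This is a one time, routine test that is performed in patients with anorectal dysfunction", and study drug is given out only at the end of the same visit.

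For continuous data, 2.18 specifies "t-tests to detect differences in group means, with Bonferroni correction for multiple comparisons". It gives no family, number of comparisons or order. It then sets 0.05 as the threshold throughout, without saying whether that applies to raw or adjusted p-values. Predictors of response go to logistic regression. The only power statement, in 2.18 and 3.12, is for the primary severity rating.

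**The concern.** The aims give one group of secondary outcomes priority, and the analysis sections do not act on it. Section 2.17 is the only list of outcomes, and 2.18 names one correction for continuous data. An analyst could reasonably take the whole list as the family. PAC-QOL and FIQL would then share their error rate with every other numeric variable, including manometry values that cannot respond to treatment because they are recorded before the first dose.

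An analyst could equally take a family of two, or of the five questionnaires. With the count unstated, whether a quality-of-life result is significant could depend on a choice made after the data are seen.

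Separately, plain Bonferroni gives up power for nothing in return. Holm's step-down procedure controls the same family-wise error rate, needs no further assumption, and rejects every hypothesis that Bonferroni rejects.

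**Working it through.** **Inputs from the plan (2.18, 3.12).** The design is "with a power of 0.80, alpha=P<0.05 in a two-tailed analysis", sized to "detect at least a 3 point reduction in symptom severity". On spread, "we took a conservative estimate with an expected standard deviation of 4 points", while "similar research studies using patient-reported outcomes have reported standard deviations ranging around ~2.5 points". The plan needs 28 per arm and enrols 70 in total (35 per arm).

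**The plan's own figure.** Normal approximation, n per arm = 2(1.960 + 0.842)² × 4²/3² = 27.9, so 28. Drop-out: 56/0.80 = 70. Both reproduce. With the planned t-test, power at 28 per arm is 0.787.

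**Assumptions not in the plan.** No effect size or SD is given for PAC-QOL or FIQL. I borrow the primary's standardised difference, d = 3/4 = 0.75, and vary it. The upper value is d = 3/2.5 = 1.2, from the plan's other SD; d = 0.5 is my lower value. Each questionnaire counts as one score.

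**Counting the family (m).**
- Three diary measures + five questionnaires = 8 outcome scores.
- Adding compliance and five numeric manometry measures (first sensation, urgency, pain, resting pressure, squeeze pressure) = 14.
- PAC-QOL and FIQL alone = 2.

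**Bonferroni power per outcome.** Two-sided t-test at level 0.05/m, degrees of freedom 2n − 2, noncentrality d√(n/2). At n = 28 and d = 0.75 the noncentrality is 0.75 × √14 = 2.806. The critical values are 2.005 (m = 1), 2.306 (m = 2), 2.846 (m = 8) and 3.047 (m = 14).

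| n per arm | d | m = 1 | m = 2 | m = 8 | m = 14 |
|---|---|---|---|---|---|
| 28 | 0.5 | 0.45 | 0.34 | 0.18 | 0.13 |
| 28 | 0.75 | 0.79 | 0.69 | 0.49 | 0.41 |
| 28 | 1.0 | 0.96 | 0.92 | 0.81 | 0.75 |
| 28 | 1.2 | 0.99 | 0.98 | 0.95 | 0.92 |
| 35 | 0.75 | 0.87 | 0.80 | 0.62 | 0.55 |

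**Holm against Bonferroni.** Simulation, 28 per arm, d = 0.75 where an effect exists, correlation between scores 0.3 and 0.6:
- Two key outcomes, both affected: Holm about 0.75 each, Bonferroni 0.69.
- Two key outcomes, one affected: Holm 0.69, the same as Bonferroni.
- Eight scores, all affected: Holm 0.60 to 0.61, Bonferroni 0.49.
- Eight scores, half affected: Holm 0.52, Bonferroni 0.49.
- Two key outcomes by Holm, tested only if the primary is significant, with all three at d = 0.75: about 0.62 to 0.66 each.

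**The case against.** The strongest reply is that the plan does not commit to a correction over 8 or 14 tests. That is right. A reader might infer from 2.17 and 2.18 together that one flat Bonferroni covers everything listed, but 2.18 does not say so. A family of 14 is the least natural reading, since Aim 2 uses compliance and manometry to explore what is associated with response, and 2.18 gives that task to logistic regression. What the documents show is an undefined family.

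A reader might also infer that power for quality of life is 0.41 to 0.49, so that a real benefit would more often be missed than found. The documents do not support that as a fact about the trial. The 0.75 comes from a different scale, with an SD that the plan itself calls conservative. At d = 1.2, power stays above 0.9 even with 14 tests; at d = 0.5, it is below one half with no correction at all. Equal effects on both instruments are also uncertain: 3.13 admits patients with constipation, incontinence or both, and 1.3 calls mixed forms less common, so many patients may have little to gain on one scale.

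Finally, Bonferroni is valid. Choosing Holm is an improvement and does not correct an error, and the gain is small (0.52 against 0.49 over eight scores) when only half the scores are affected.

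None of this accounts for the lost ranking, or for a pre-dose test being listed as an end point.

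**Conclusion.** The point holds in conditional form. Three things follow from the documents without any power assumption: Aim 2's key status is not carried into 2.17 or 2.18; a one-time pre-dose measurement is listed as an outcome; and the Bonferroni family is undefined.

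The cost in power rests on assumptions. With d = 0.75, 28 per arm and a correction over 8 to 14 tests, power per key outcome is 0.49 to 0.41. It would be 0.69 with Bonferroni over two, and about 0.75 with Holm over two if both effects are real (0.69 if only one is). Across d from 0.5 to 1.2, power at 8 to 14 tests runs from 0.13 to 0.95. The primary test and its sample size are not affected.

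**What to change.** 1. In 2.17, mark change in PAC-QOL and change in FIQL as the key secondary end points, matching Aim 2.
2. In 2.18, replace Bonferroni with Holm. Test the two key outcomes as their own Holm family at two-sided 0.05, and say that the threshold applies to adjusted p-values.
3. Move compliance and pre-dose manometry out of the tested outcomes and into the logistic-regression predictors, as Aim 2 intends.
4. State how the remaining secondary scores (PAC-SYM, FISI, SF-36 and the diary measures) are handled: either a second Holm family, or estimates with 95% intervals reported as supportive.

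This changes wording only and adds no patients, visits or data. Replacing Bonferroni with Holm in a given family has no downside. The separate key family has one, which step 4 must settle. With a second family at 0.05, error is controlled within each family and not across both (at most 0.05 + 0.05 = 0.10 overall). With supportive reporting, those scores carry no formal significance claim.

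Testing the key outcomes only after a significant primary is optional and not part of this fix. It would lower power per key outcome to about 0.62 to 0.66 under the same assumptions, and a failed primary would leave quality of life formally untested.
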